# **S**YNOPSIS

31NUP313	
ΗΥΡΟΤΗΕSIS	Analytical interruption of longstanding antiretroviral therapy (ART) in HIV-1 infected patients with a very low proviral reservoir results in "functional cure".
DESIGN	Prospective observational study.
STUDY SITE & POPULATION	HIV-1 infected patients with normal peripheral blood CD4 T-cell counts and undetectable viral load will be recruited in four Belgian HIV reference centers: Institute of Tropical Medicine Antwerp, University Hospital Ghent, University Hospital Brussel, Saint-Pierre University Hospital.
DURATION	9 months screening + 48 weeks clinical study + 12 weeks post study. (23 months in total until last patient visit)
OBJECTIVES AND ENDPOINTS	The primary objective is to evaluate the proportion of patients with low proviral reservoir that have a sustained viral suppression after 48 weeks of treatment interruption.
INCLUSION & EXCLUSION CRITERIA	HIV-1 infected adults with peripheral blood CD4 T-cell counts >= 500/μL and plasma viral load < 50 copies/ ml will be evaluated for inclusion. HBV or HCV co-infected patients and patients with ongoing HIV-related diseases or a history of antiretroviral drug resistance or AIDS event will be excluded.
SCREENING, RECRUITMENT & RANDOMIZATION	Two-step screening: viral reservoir measurement and analytical treatment interruption. There is no randomization foreseen
INTERVENTION	Interruption of antiretroviral treatment in HIV-1 infected patients with low viral reservoir.
FOLLOW-UP	Intensive clinical and laboratory follow-up during 48 weeks followed by 12 weeks post intervention.
ANALYTICAL METHODS	Total HIV PCR for plasma viral RNA, for cell- associated viral RNA and DNA will be quantified using droplet (digital PCR droplet). Viral outgrowth assay (limiting dilution culture of CD4 T cells).
SAFETY	Safety of the intervention will be evaluated by recording (Serious) Adverse Events and grading laboratory parameters and vital signs. Data will be monitored by means of a sponsor regulated pharmacovigilance system.

# **1.** INTRODUCTION

# 1.1 Background

Combined antiretroviral treatment (cART) induces a rapid decline in HIV plasma viral load (pVL), which after several years of cART reaches a plateau of 1-10 copies per ml plasma [1]. Nevertheless, proviral DNA, which represents the HIV reservoir, may persist at levels of hundreds or thousands of copies per million CD4-T cells in peripheral blood. The establishment of this proviral reservoir is complex and involves, among others, naïve, central memory, transitional and effector memory T cells [2].

The HIV reservoir is widely distributed, not only in blood, but also in lymphoid organs, the central nervous system, the intestinal tract and genital organs [3–5]. Measuring proviral DNA for clinical purposes can readily be performed on peripheral blood mononuclear cells (PBMC), CD4-T cells or subsets thereof. The magnitude of the proviral DNA reservoir is not necessarily predictive for the occurrence and extent of viral rebound following cART interruption since a high proportion of integrated HIV DNA has been shown to be replication incompetent in viral outgrowth assays (VOA) [6]. Therefore, quantifying the replication capacity of the HIV reservoir, by optimally stimulating CD4+ T cells in a limiting dilution VOA, currently represents the most reliable ex vivo parameter of viral fitness[7,8]. Cellassociated unspliced HIV RNA (usRNA) has recently been proposed as a marker/indicator of residual viral transcription in cART-treated subjects with pVL below the targeted clinical limit of 50 copies/ml. Indeed, slightly elevated levels of PBMC-associated usRNA among patients with pVL below detection level but with suboptimal treatment adherence were shown to be predictive of therapy failure in the future [8]. Cell-associated viral DNA, usRNA and viral outgrowth capacity need therefore to be evaluated in the development of novel HIV therapeutic strategies.

HIV research is challenged by the concept of inducing "functional cure" or HIV remission, i.e. interventions aiming at keeping the viral load at low or undetectable levels after interrupting cART in infected patients. It has been suggested that so called "elite controllers" (EC) may provide important clues in this quest [9]. By definition EC are able to maintain their pVL "spontaneously" below the lower limit of detection i.e. without ever being treated with cART (or other regimens) [10,11]. Importantly, reports have recently emerged describing patients maintaining pVL below the lower limit of detection after interruption of long-time cART. These patients have been referred to as "secondary controllers" [12] or "post treatment controllers" (PTC) [13]. Conceptually, this status may provide additional and potentially more relevant information to develop strategies aiming at HIV cure.

The undetectable pVL in EC has been shown to be associated with low proviral DNA in peripheral blood CD4+ T cells and other reservoirs (e.g. the gut-associated lymphoid tissue) and with low or absent intracellular viral RNA. Some genetic host factors (e.g. the HLA types B27 and B57) as well as viral genetic characteristics (e.g. defects in Nef, Vif or other genes) are known to be associated with the EC phenotype. In the majority of the EC, HIV-specific CD8+ T- cell response has been shown to be qualitatively superior to the response seen in progressors. With this regard, HIV-specific CD8+ T cells targeting conserved viral proteins (e.g. Gag), exhibiting a polyfunctional cytokine production pattern, recognizing a broad array of epitopes and/or characterized by a high avidity have been shown to correlate with a better clinical outcome. However, the most consistent finding in EC is the presence of CD8+ T cells with a high "virus-suppressive/cytolytic" activity. Consequently, even in the absence of viral genetic defects, the replication capacity of HIV strains isolated from EC has been shown to be lower than what is seen in progressors [14].

Several large studies in chronically HIV infected subjects showed that interruption of longterm cART not only resulted in prompt rebound of plasma viremia but was also clinically harmful in the long-term, especially when performed repetitively in subjects with low nadir CD4+ T cells [15,16]. However, observational studies [17–20] and clinical trials [21,22] evidenced that interruption of cART that was initiated during primary HIV infection (PHI), resulted in delayed viral rebound and disease progression [23]. Interestingly, in some of these patients, pVL remained below the lower limit of detection during many months or years post treatment interruption (TI). Steingrover et al. identified 4 out of 24 patients initiating cART during PHI, who maintained pVL < 50 copies/ml for at least 48 weeks after interruption of long-term cART [24]. In analogy, Hocqueloux et al. described 5 out of 32 PHI patients with VL < 50 copies/ml for a median of 75 months after TI [25]. Within the French ANRS PRIMO cohort, 164 patients interrupted cART that was initiated during PHI. pVL remained <50 copies/mL in 14/164 subjects for a median of 4.5 years [26]. Additional PTC were described in the European seroconverter CASCADE cohort [27]. However, these cohorts of PTC do not provide insight in the underlying immune and/or viral mechanisms contributing to the control of viral replication post TI.

Although no viral rebound (i.e. (pVL> 400 copes/ml) was documented in the 14 PTC described in the French VISCONTI cohort, six of these patients showed intermittent blips in pVL (i.e. pVL elevation between 50 and 400 copies/ml) during the 48-113 months of TI. In contrast with EC, the CD4+ and CD8+ T- cell activation state as well as the HIV-specific T-cell responses were shown to be weaker in PTC. Moreover, no overrepresentation of "protective" HLA alleles (e.g. B27 and B57) was observed in this population. In addition, exvivo CD8+ T-cell mediated HIV suppressive activity, which is commonly observed with EC, was completely absent PTC population from the VISCONTI study. Importantly, the cellular proviral DNA in PTC was very low following TI. Very remarkably, the cellular proviral DNA tended to further decrease over time in the absence of cART in some of these patients. Nevertheless, HIV could be cultured in vitro from autologous CD4+ T cells of all PTC. Unfortunately, the viral replication capacity, as measured by limiting dilution (outgrowth) assay or kinetic (fitness) assay, was not evaluated [13].

Four patients followed at ITG, who initiated cART during the chronic viremic phase, durably maintained control over viral replication after interruption (for varying reasons) of long-term cART [12]. No particularities were highlighted when evaluating the HIV-specific T-cell responses. Although no HLA-association or CCR5A32 polymorphism was observed, all four PTC had a low viral reservoir when compared to non-controllers, as assessed by PBMCassociated total HIV DNA. In addition, no intracellular viral unspliced mRNA species could be measured, suggesting a status of "silent" provirus. Finally, VOA from autologous CD4+ T cells repeatedly failed in one patient and showed delayed kinetics and low fitness in two others. With respect to viral characteristics the latter secondary controllers were rather similar to EC (low proviral load, low intracellular HIV mRNA and difficult-to-culture viruses). They were also clearly different compared to viremic progressors or aviremic subjects under continuous cART (from whom HIV could be easily cultured in vitro and who had higher HIV DNA and intracellular HIV mRNA). Five years following TI and although lacking viral rebound, two PTC were restarted on cART because of low CD4+ T cell counts [12]. Similarly, the SALTO study showed that 7 out of 95 chronically-infected HIV patients were able to control viral replication below the 400 copies/mL 12 months after long-term cART interruption[28]. Again, in these patients, the only associated predictive factor for viral control in this early treated chronic population was a low level of blood cell associated HIV DNA.

Thus, recent data provide sufficient evidence that a small proportion of HIV-1 infected subjects is able to spontaneously maintain viral suppression after interruption of long-term cART. This observation challenges the common wisdom that cART needs to be taken lifelong to prevent viral rebound and disease progression [29]. Although most PTC described in the medical literature so far initiated cART in the acute phase of the infection, there is emerging evidence that some patients, who started cART in the chronic progressive phase of the infection, are also able to control viremia following TI. Based on the observations in the VISCONTI, PRIMO and SALTO cohorts it is estimated that between 5 to 15 % of patients initiated on cART at the acute phase of the disease might spontaneously control viral replication following TI [13].

Since it has repeatedly been argued that analytical treatment interruption (ATI) in selected patient subgroups may be acceptable to evaluate interventions aimed at functional cure [30,31], prospective studies looking into possible mechanisms and predictors of PTC are urgently needed. The data summarized above suggest that at least some patients with normal CD4+ T-cell, high nadir CD4+ T cells and an exceptionally low proviral load after prolonged periods of cART, initiated either in the acute or chronic phase of the disease, might spontaneously control viral replication after ATI. In depth prospective studies on clinical and laboratory characteristics, including total HIV DNA, intracellular RNA and VOA, in post-treatment controllers and non-controllers might provide clues to understand the nature of control of viral replication after ATI. Obviously, candidates for ATI should carefully be selected (e.g. to avoid HIV superinfection or other clinical complications) and closely monitored following TI, with prompt re-initiation of cART according to preset criteria. Ultimately, well-designed ATI trials might reveal modifiable factors that could inspire novel treatment strategies aiming at functional cure.

# 1.2 Rationale

Over the decennia, the face of HIV infection has changed from a fatal to a chronic disease with near normal life expectancy, provided cART is maintained. However, HIV cannot be eradicated as it persists as proviral DNA in long-lived host cells, mainly memory CD4+ T cells. Therefore, in most patients, treatment interruption results in prompt reactivation of the proviral reservoir, rebound in plasma viremia to pre-treatment levels and ensuing disease progression. Hence, today, it is generally accepted that cART needs to be taken lifelong [32].

Currently, about 10 million HIV-infected patients worldwide, including around 4,000 in Flanders, are treated with cART. This number will increase as most recent guidelines recommend earlier treatment initiation, given the benefits of cART in terms of blocking disease progression, prevention of transmission and reducing co-morbidity [33]. Moreover, despite major improvement in antiretroviral drug efficacy, tolerability and pill burden, several drugs, especially protease inhibitors and nucleoside analogues, are associated with long-term toxicities[34].

In addition to the cumulative cART toxicity, the difficulties to access treatment in some areas of the world, the dislike expressed by patients about livelong drug use on a daily base, the development of drug resistance and the cost associated with life-long cART, create an urgent need for an HIV cure. Complete elimination of HIV proviral DNA reservoir (also known as "sterilizing" cure) has so far possibly only been accomplished in one patient, also known as the "Berlin patient"[35]. Strategies towards a "functional" HIV cure (i.e. very low HIV reservoir and sustained control of viremia in the absence of cART) are currently being

developed [36]. These strategies remain however experimental and might need years before entering into clinic [37].

Interestingly, we and others have observed that a small proportion of patients, with longstanding cART history, were able to spontaneously control viral replication for a long period of time following TI [12]. An exceptionally low proviral DNA reservoir was shown to be a common characteristic of these PTC. Very low or absent viral replication capacity (as measured by intracellular HIV RNA and ex vivo outgrowth assay) might also be involved in the PTC phenotype. Eventually, these recently identified PTC may constitute an interesting model towards functional HIV cure [38].

To our knowledge, so far, no clinical trial has been performed prospectively to quantify the viral reservoir in order to identify patients in whom cART could safely be interrupted. We will therefore prospectively evaluate about 640 cART treated HIV-1 positive patients in order to select a subgroup of individuals with extremely low HIV reservoirs, defined as an undetectable total HIV DNA and cell-associated HIV RNA (see section 5.1.3 for details) (first strategic goal). In those patients harboring low HIV reservoir, an analytical treatment interruption will be proposed (second strategic goal). Clinical and laboratory parameters (including VOA at baseline) of ensuing controllers and non-controllers (PTC vs. non-PTC) should allow us to identify predictors of functional cure after ATI (third strategic goal).

The innovative approach taken in this trial should help to take decisions on interrupting cART in future HIV cure strategies and lead to the identification of clinical and laboratory parameters correlating with PTC.

# 2. STUDY DESIGN

# 2.1 General study design

This is a single arm multi-centric non-randomized (prospective) study. The participants will be included step-wise. The study will be divided in two parts. The first one will aim at quantifying the HIV reservoir in a large group of patients under ART with strictly predefined inclusion and exclusion criteria. The second step encompasses an analytical treatment interruption among participants with the lowest viral reservoir. Both steps will be subjected to a specific informed consent procedure.

# 2.2 Sub-studies

Sub-studies will be implemented concurrently with the main study pending approval by the steering committee.

A laboratory committee will be set up to overlook and monitor the organization of the substudies. This committee will be composed of one investigator from each of the participating center and will advise the steering committee on the prioritization of ancillary projects.

Separate approval of the sub-study protocol has to be obtained from the institutional review board (IRB) of the Institute of Tropical Medicine (ITM) and the relevant independent ethics committees (IECs). A separate informed consent procedure will be required in case of extra sampling or procedures.

# **3. STUDY OBJECTIVES**

The project hypothesis is that treatment interruption (TI) of longstanding combined antiretroviral therapy in participants with a very low proviral reservoir results in "functional cure".

The **primary objective** is to determine the proportion of post treatment controllers (PTC) i.e. patients under cART with low baseline peripheral blood proviral DNA that will show sustained viral suppression at 48 weeks post TI.

The secondary objectives are:

Confirmation of the safety of a TI strategy in selected HIV patients

Assessment of the viral reservoir magnitude prior and after TI

Assessment of viral and host dynamics in those participants with viral rebound post TI. The **exploratory objective** is:

Identification of predictors (clinical and/or laboratory) of PTC phenotype

# 3.1 Primary endpoint

Assessment of the proportion of participants with pVL below the lower limit of detection (<50 HIV RNA copies/ml plasma) 48 weeks following interruption of antiretroviral treatment.

### 3.2 Secondary endpoints

1) Safety of interrupting antiretroviral treatment will be reported according to the Common Terminology Criteria for Adverse Events (CTCAE), version 4.0.

2) Evaluation of the reservoir replenishment upon interruption of antiretroviral treatment by quantifying the viral reservoir at baseline (i.e. just before TI), during TI and at viral rebound.

3) Assessment of the kinetics of HIV viral load rebound after TI based on the repetitive pVL measurements.

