### Definition of an Adverse Event

An Adverse Event (AE) is generally described as any untoward medical occurrence in a subject or clinical investigation subject administered a pharmaceutical product and that does not necessarily have a causal relationship with this treatment. An AE can therefore be any unfavorable and unintended sign (including an abnormal laboratory finding), symptom, or disease temporally associated with the use of a medicinal (investigational) product, whether or not related to the medicinal (investigational) product.

However, this definition does not entirely fit the purpose of this study, because we will not assess a pharmaceutical product. Therefore, we will consider the intervention (=interruption antiviral treatment) as the pharmaceutical product under investigation and will adapt the definition accordingly:

An Adverse Event (AE) is generally described as any untoward medical occurrence in a subject or clinical investigation subject with treatment interruption and that does not necessarily have a causal relationship with the treatment interruption. An AE can therefore be any unfavorable and unintended sign (including an abnormal laboratory finding), symptom, or disease temporally associated with the treatment interruption, whether or not related to the treatment interruption.

Once treatment interruption has started, until the end of study, clinic staff will enquire about common possible side effects based on the "division of AIDS table for grading the severity of adverse events (see annex)" and will ascertain the occurrence of any adverse events since the last visit. All of them, including clinically significant laboratory abnormalities, will be recorded in the electronic Case Record Form (eCRF) and categorized in terms of severity, relationship to ARV interruption, outcome and seriousness, throughout the study duration. Episodes of viral acute syndrome, possible events of special interest, all serious adverse events (SAEs) and all the events leading to participants' withdrawal from the study will be monthly communicated to the Scientific Advisory Board.

All the events will be followed up till resolution, except those at the final end of study (=end of follow-up period).

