### Severity, relationship of event to ARV interruption and outcome

- 1. *Mild:* events require minimal or no treatment and do not interfere with the subject's daily activities.
- 2. *Moderate:* events result in a low level of inconvenience or concern. Moderate events may cause some interference with functioning.

- 3. *Severe:* events interrupt a subject's usual daily activity and may require systemic drug therapy or other treatment. Severe events may be temporarily incapacitating.
- 4. Life-threatening: Subject at risk for death at the time of the event

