### Assessment of causality

The investigator will assess the relationship between the ARV interruption and the occurrence of each AE/SAE. A list of expected adverse event is given. In addition, the investigator will use clinical judgement to determine the possible relationship of other (not expected) events.

The relationship of an adverse event to ARV interruption is to be assessed according to the following definitions and can only be done by the study physician:

- 1. **Definitely unrelated**: Reserved for those events which cannot be even remotely related to ARV interruption (e.g. injury caused by a third party).
- 2. Unlikely: There is no reasonable temporal association between the ARV interruption and the AE, the AE is not expected (according to a pre-defined list) and the event could have been linked to other known reasons.
- 3. **Possible**: The suspected AE may or may not follow a reasonable temporal sequence from ARV interruption but It is not fully unexpected but it could be linked to other known reasons.
- 4. Likely: The suspected adverse event follows a reasonable temporal sequence from ARV interruption. Either it is expected (according to based on the "division of AIDS table for grading the severity of adverse events) or it is likely caused by ARV interruption in the investigator's judgment.
- 5. **Definitely related**: Reserved for those events which have no uncertainty in their relationship to ARVs interruption.

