4.1. Primary Objective

The primary objective will be assessed by estimating the proportion of participants with undetectable viral load (<50 HIV RNA copies/ml plasma) 48 weeks after interruption of ART. A 95% CI for the proportion will be calculated using Wilson's score method (Example Table 3). Respective proportions at different time points (week 2, 4, 6 and 8) will be also calculated for descriptive purposes.

4.2. Secondary Objectives

Adverse events (AEs) will be coded using the Medical Dictionary for Regulatory Activities (MEDDRA) and will be reported based on MEDDRA preferred terms and body systems. All AEs will be analyzed based on counts of patients with a specific category and not on counts of individual adverse events. The relationship between AEs and ARV interruption is determined by the investigator and categorized as "drugrelated" if unlikely, possibly, likely or definitely related to treatment interruption. All AEs definitely unrelated to intervention will also be used to examine the relationship between AEs and intervention.

All AEs and all serious AEs from the beginning of treatment interruption until the end of the study (end of follow-up period) are reported. AE counts will be summarized for the whole study period (treatment interruption and follow-up period). Counts (%) of patients with AEs, drug-related AEs and serious AEs will be presented by Meddra body system and preferred term together with a 95% Wilson confidence interval (Example Table 4 and 5).

Reservoir replenishment and HIV viral load kinetics following ART interruption will be summarized in terms of medians and interquartile ranges (Example Table 3). No formal statistical testing will be done in these results. If present, pVL rebound will be represented graphically with a spaghetti plot. Furthermore, the measurements over time of viral load rebound and viral reservoir will be presented graphically for every patient included in the study (one line for every patient over time).

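### The safety endpoint names CTCAE v4.0, the safety section points to the DAIDS table and to a separate four-level scale, and no planned table reports severity

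*Protocol*

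**What the plan says.** **Endpoint.** Protocol 3.2, secondary endpoint 1: "Safety of interrupting antiretroviral treatment will be reported according to the Common Terminology Criteria for Adverse Events (CTCAE), version 4.0". This is the only mention of CTCAE in either document.

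**Collection.** Protocol 7.1 (Definition of an Adverse Event) has clinic staff ask about common possible side effects using the "division of AIDS table for grading the severity of adverse events (see annex"). Every AE goes into the eCRF, "categorized in terms of severity, relationship to ARV interruption, outcome and seriousness". Annex 3 is a web link to the DAIDS table, with no version stated. No CTCAE annex exists.

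**Scale written out.** The next subsection of 7.1 lists four numbered levels: mild, moderate, severe and life-threatening. They are defined by effect on daily activity, need for treatment and risk of death; the top level is "Subject at risk for death at the time of the event". Neither CTCAE nor DAIDS is cited there.

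**Laboratory and vital signs.** The synopsis and the opening of 7.1 say that these will be graded.

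**Analysis.** Protocol 8.3.4 evaluates safety by AE and SAE percentages with Wilson 95% intervals. SAP 2.3 and 4.2 do the same, coding in MedDRA: "All AEs will be analyzed based on counts of patients with a specific category", that is, by patient and not by event. Example Table 5 has four rows: any AE, any intervention-related AE, any SAE and any intervention-related SAE. Example Table 4 and its parallel tables use body system and preferred term. None has a severity column or row.

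**The concern.** Three severity references are in play and nothing says which one governs. Four sites could apply different ones and still follow the protocol. Whichever they apply, the severity they record reaches no planned output.

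This matters because the safety objective in Protocol 3 is to confirm that interruption is safe in selected patients, and the protocol states its own expectation in terms of severity. Section 11.1 expects rebound in most participants and clinical signs of mild to moderate degree in some of them. As planned, the tables cannot show whether events stayed within that range. Seriousness does not stand in for severity: an event that stops a participant's usual activities for a time is severe on the protocol's scale, yet it need not meet any of the SAE criteria in 7.1.

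**Working it through.** This is mainly a comparison of texts, with a short calculation to show what is lost.

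**1. Which scale?**

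| Place | Reference | Stated use |
|---|---|---|
| Protocol 3.2 | CTCAE v4.0 | Reporting of safety |
| Protocol 7.1, Definition of an Adverse Event; Annex 3 | DAIDS table, no version | Prompt for enquiry |
| Protocol 7.1, Severity | Four generic levels | Severity of each AE |
| Protocol 7.1, Assessment of causality | DAIDS table | List of expected events |
| SAP 4.2 | MedDRA | Coding of terms |

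No statement links any of these to another. The four-level scale contains no laboratory thresholds, so the promised laboratory grading must come from some other table, and the documents do not say which.

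**2. Does another reading of 3.2 remove the conflict?** If reporting according to CTCAE means terminology and not grade, the SAP still names only MedDRA and does not say how CTCAE comes in. Endpoint 1 is unmet as worded on either reading.

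**3. Does the related row separate the events that matter?** Protocol 7.1 has five causality categories. SAP 4.2 counts four of them as related, including unlikely. Only definitely unrelated events drop out, so this row will discriminate little.

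**4. The plan's own precision figure.** Protocol 8.4 gives a Wilson 95% interval width of 18 to 25 points for 32 participants. With p = x/n, n = 32 and z = 1.960:

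- centre = (p + z²/2n) / (1 + z²/n)
- half-width = z × √(p(1−p)/n + z²/4n²) / (1 + z²/n)
- 2/32: 1.7% to 20.2%, width 18.4 points
- 5/32: 6.9% to 31.8%, width 24.9 points

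Using the counts of 2 and 5 from Protocol 4.3, the stated range is reproduced. The safety rows use the same method.

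**5. What Table 5 would show.** Assume, for illustration only, that 16 of 32 participants have an AE, that all these AEs are related and that none is serious. Compare two cases: all mild, or all severe.

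| Row | All mild | All severe |
|---|---|---|
| Any AE | 16/32, 50% (33.6 to 66.4) | the same |
| Related AE | 16/32, 50% (33.6 to 66.4) | the same |
| SAE | 0/32, 0% (0 to 10.7) | the same |
| Related SAE | 0/32, 0% (0 to 10.7) | the same |
| Severe or life-threatening AE (not planned) | 0/32, 0% (0 to 10.7) | 16/32, 50% (33.6 to 66.4) |

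With the same preferred terms, Table 4 is also identical in the two cases. The count of 16 is arbitrary: the four planned rows would agree between the two cases at any count.

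**The case against.** The strongest reply is that the SAP took nothing away. Protocol 8.3.4 already defines the planned safety result as AE and SAE percentages, and SAP 4.2 and Table 5 deliver exactly that; 3.2 never uses the word grade. This stands against any claim that the SAP dropped a graded analysis planned in the protocol. It does not reconcile 3.2 with 8.3.4, and it does not explain why severity is collected.

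A reader might infer that AEs are graded with the DAIDS table. The text does not say so. It uses the table to prompt enquiry and as a list of expected events; a grading role is only suggested by the table's title, the annex and the severity sentence that follows. Neither CTCAE nor DAIDS criteria are reproduced, so it cannot be shown from the documents that an event would be classed differently under the two.

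Harm would also not go unseen. Table 4 lists events by preferred term. SAEs include important medical events. Acute viral syndromes, SAEs and events leading to withdrawal go monthly to the Scientific Advisory Board. That is correct, but none of these routes gives a count of patients by severity.

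**Conclusion.** The point holds as a reporting inconsistency in one descriptive secondary endpoint. Endpoint 1 is not met as worded, because the scale it names is used nowhere. Severity is recorded for every AE and laboratory and vital-sign grading is promised, but no planned output shows either. Severe non-serious events therefore cannot be told from mild ones, and the protocol's expectation of mild to moderate signs cannot be checked.

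Two stronger readings should be set aside. One is that safety cannot be reported at all: AE and SAE percentages with Wilson intervals need no severity scale and remain deliverable. The other is that nearly everyone will have some AE over 60 weeks, which would empty the any-AE row of meaning. The documents give no AE rate, and no row is designated as the main one. Sixty weeks is the maximum, for participants with sustained suppression (Protocol 5.1.9); those who rebound are followed for 12 weeks from restart of cART (5.1.8). With control expected in 2 to 5 of 32, some 32 − 5 = 27 to 32 − 2 = 30 participants could have shorter follow-up.

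The conclusion assumes that the eCRF records severity as 7.1 requires; the eCRF itself is not among the documents. The primary analysis and sample size are unaffected.

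**What to change.** 1. **Protocol 3.2, 7.1 and Annex 3:** name one severity scale, with its version, that matches what the eCRF records. State whether the four written levels are that scale or are replaced by it. If the DAIDS table is kept only as a prompt and as the expected-event list, say so; if it is removed, the causality definition that relies on it needs a new reference.
2. **SAP 2.3, 4.2 and Table 5:** add the number of patients (%, Wilson 95% CI) with any AE, and with any intervention-related AE, that is severe or life-threatening (levels 3 and 4 of the protocol's list). Include graded laboratory abnormalities. A table of patients by maximum severity would serve equally well.
3. **Vital signs:** add an output for the promised grading, or state that none is planned.
4. **If sites have already used different scales,** record in the SAP which was used where.

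The cost is a few table rows and a wording change, which under Protocol 11.3 goes through the amendment process. No new AE data are needed. If laboratory grades are not held in the eCRF, they would have to be derived from the scheduled laboratory results.
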